8.4.1 Study Time and Events Table

[figure not shown]
Study timeline (calendar time, H1=January-June, H2=July-December):

	2018	2018	2019	2019	2020	2020	2021	2021	2022
	H1	H2	H1	H2	H1	H2	H1	H2	H1
Planning									
Enrollment									
Outcome tracking									
Analyze impact									
Manuscript preparation									

[figure not shown]
Study timeline (subject point of view):

[figure not shown]
Treatment							
Study Activity	Enrollment	Month 6	Month 12	Month 24			
Informed Consent ¹	Х						
Randomization	Х						
FFF Program Initiation ⁵	Х						
Survey ³	Х	Х	Х				
Research Labs ⁴	Х	Х	Х				
Health Care Utilization Review (EMR)	X						

Control							
Study Activity	Enrollment	Month 6	Month 12	Month 24			
 ¹ Patients will be asked to provide verbal consent over the phone. ² FFF program start will occur approximately 6 months after consent for Control patients. ³ Redcap surveys will be administered by FFF staff during program visits. ⁴ Research labs include: HbA1c, Fasting Glucose, lipid panel ⁵ FFF program start will occur within 1 month after consent for Treatment patients. 							
Research Labs ⁴ X X							
Health Care Utilization Review (EMR)	X						

8.4.2 Study Flow Diagram

8.5 Primary Endpoints

The primary endpoint will be HbA1c at 6 months. HbA1c is the primary measure for diabetes diagnosis and disease progression. We explored the existing literature on the link between A1c and spending. The literature is largely a set of correlations: reductions in A1c are associated with lower costs in patients with diabetes. In summary, improving A1c from poor to fair is associated with savings on the order of \$1000 per year (sustained over time). As expected, the effects are nonlinear so that larger cost savings are achievable for those with A1c > 9 compared to those between 7 and 8.

[figure not shown]
Justification

HbA1c is meaningfully related to health and healthcare utilization. Elevated levels are often noted to increase healthcare costs by \$4000. Menzen et al. (2010) controlled for a number of characteristics and estimated healthcare costs were \$4000 higher over five years for those with A1c>10 compared to those with A1c <7.²³ Juarez et al. (2013) used propensity score matching to control for differences across patients and found that having an A1c>=7 was associated with \$2700 higher medical costs per year compared to those with A1c<7. Importantly, the relationship is nonlinear with larger savings for patients with the higher levels of HbA1c considered here.²⁴

In Canada, McBrien et al. (2013) also find that, among diabetics, annual medical costs rise in a nonlinear fashion with A1c: C\$27,064 for those with A1c $\leq 7\%$, C\$26,736 for those with A1c of 7.1 – 7.9%, C\$28,687 for those with A1c of 8-9%, and C\$32,629 for those with A1c>9%.²⁵

Where many studies compare utilization across patients with different levels of A1c and control for patient characteristics in various ways, Wagner et al. (2001) took the approach of comparing changes in utilization with changes in A1c at the individual level. This controls for fixed characteristics of the person that would otherwise be difficult to control, such as education level, stable attitudes toward health.²⁶ They define an improvement as a 1 percentage point reduction that is sustained for 2 years. Among those who achieved this improvement, healthcare costs were approximately \$900 lower each of the following two years (or approximately \$1440 in

CONFIDENTIAL AND PROPRIETARY

2017 dollars). This included a 2-percentage point reduction in hospitalization rates each year, compared to a 15% hospitalization rate overall.

Other studies look at disease management impacts on A1c and costs or drug adherence programs on costs. One relatively large observational study is Oglesby et al. (2006), where direct medical costs attributable to type 2 diabetes were 16% lower for individuals with A1c<7 compared to those with A1c >7 and < 9, and 20% lower for those with A1c <7 compared to those with A1c > 9.2^{7}

[figure not shown]
8.6 Secondary Endpoints

We will also examine HbA1c at 12 months, where we can compare 12 months of exposure to the program compared to 6 months of exposure to the program. This difference will be smaller if the gains in A1c improvement are greater during the initial 6 months, as expected. The comparison will help us learn the rate of improvement over time. In addition to 6- and 12- month results, we will also consider interim lab results in the patient's EHR record to trace out the timing of effects.

In addition, related measures that may be affected by the program: Fasting glucose, weight, BMI, blood pressure, and lipid panel. Reductions in BMI among patients with diabetes are associated with lower health care costs ([name] et al., 2015).²⁸

Utilization is also an important secondary input. This will be measured using EHR data and claims data from Geisinger Health Plan for those participants who are members. Highmark (another local insurer) may share utilization data for their patients that are participating in the program as well. In particular, ED visits, inpatient care, and outpatient visits will be considered. In addition, the EHR data will allow us to determine whether a subject completes wellness visits in terms of PCP and endocrinologist visits along with diabetes Healthcare Effectiveness Data and Information Set (HEDIS) measures, as another set of healthy behaviors that may be improved as a result of program participation. We will measure

CONFIDENTIAL AND PROPRIETARY

clinical measures and utilization measures for subjects' household members as well to measure spillover effects.

A third set of secondary outcome measures will come from the patient surveys conducted. Each question will be analyzed and compared across treatment and control groups similar to the lab results. The categories are food choices, healthy behaviors, self-assessed health, and patient satisfaction.

Additionally, we will include program participation outcomes to measure treatment intensity: visits to pick up the food, use of dietician services, and food choices.

9 STATISTICS

[figure not shown]
Statistical analysis will be conducted by our co-investigators: [name], PhD; [name], and [name]. This academic team is supported by the Jameel Poverty Action Lab (J-PAL) at MIT, which specializes in randomized-controlled trials in healthcare delivery.²⁹

9.1.1 Statistical Analysis Plan

For both specific aims, we will estimate intent-to-treat models using Ordinary Least Squares regression. Consider an outcome, Y_i , such as HbA1c, for each subject i. The estimating equation is:

$$Y_i = \beta_0 + \beta_1 1 (\text{Treatment})_i + \beta_2 X_i + \varepsilon_i$$

For the historical data analysis, $1(\text{Treatment})_i$ is an indicator variable equal to one if the subject participated in the FFF program, and zero otherwise. For the prospective trial analysis, $1(\text{Treatment})_i$ is an indicator equal to one if the subject was randomized to the treatment group and zero if the subject was randomized to the control group; X_i is a vector of control variables. These control variables should be uncorrelated with the treatment indicator, but they can aid in

[figure not shown]
the precision of the estimate. We propose standard demographic and prior-utilization controls: age (5-year age bins), sex (indicator that the patient is male), race/ethnicity (indicators for African American and Hispanic), as well as the most recent outcome recorded prior to enrollment (HbA1c at the baseline visit). We will also include controls for the timing of the tests, including the number of days from baseline to the test and the month-year of enrollment in the study.

The coefficient β_1 measures intent-to-treat: the causal effect of being randomized into the treatment group. This can differ from the effect of the program if there is non-compliance: some subjects in the treatment group may decide not to join the program or join for a very short time. At the initial pilot site, 17% of those who begin the program are no longer in the program at 6 months. We plan to record outcomes for all subjects regardless of program participation and will estimate the equation using Two Stage Least Squares (2SLS), with the initial treatment assignment used as an instrumental variable for ultimate assignment. The 2SLS estimate measures the average causal effect of the program for those who choose to remain in it as a complementary parameter to the intent-to-treat analysis. In addition, if there is differential attrition from the study across treatment and control groups—despite our efforts to obtain outcomes from each subject including obtaining multiple forms of contact information for subjects and their family members and compensation for subjects' time, we will explore bounding estimates under a range of assumptions about effect sizes for those not observed.

For survey responses, we will consider answers in the top and bottom categories as separate outcomes and will test robustness to using nonlinear estimators. For patient satisfaction, we will calculate the net promoter score as an outcome as well. To avoid concerns about multiple hypothesis testing, each category of questions will be compiled into an index and we will report p-values corrected for the multiple tests when presenting results for each question individually.

In addition to outcome comparisons across all of the participants, we will consider heterogeneous treatment effects in three ways. First, a priori we are interested in whether the program is

CONFIDENTIAL AND PROPRIETARY

[figure not shown]
especially effective for different levels of baseline HbA1c to help target the program going forward. For example, if effect sizes decrease with the baseline, we may want to expand the program into those with A1c > 7.5. Next, we are interested in whether the program has different effects across the two locations where the expansions are planned to begin to investigate the external validity of the estimates. Third, we plan to consider whether machine-learning techniques to allow the data to shed light on the types of patients where the effects are particularly large are feasible with the given sample size and statistical power. This will likely entail normalizing the outcomes so that we measure effects relative to each participant's baseline rather than absolute differences.

Interim results from the trial will be monitored on an ongoing basis by the MIT/J-PAL researchers (Drs. [name], [name] and [name]), while the clinician team will be blinded from these interim results so that such do not affect program management in a way that would not be feasible outside of the study setting. Such blinding adds credibility to the results so that they are more likely to apply to other programs in the future that are not part of a study.

9.1.2 Statistical Power and Sample Size Considerations

Using data for current (i.e. self-selected, non-randomized) FFF participants, we conducted parametric power calculations. These take into account the increase in power from controlling for baseline characteristics, but qualitatively results were found when we did not include controls and when we used nonparametric (simulation) methods to estimate power. Similar results were also found when we based the calculations on similar patients in the counties where the two new sites (Lewistown and Scranton) will be located. All power calculations were conducted using STATA Version 15.

The table below shows that with the expected sample size of 500 we will have substantial power to detect small minimal detectable effects (MDE), as well as the ability to conduct heterogeneity

analyses for the clinical outcomes. For utilization outcomes, we will have power to detect the (albeit) large reductions in utilization found in the observational literature.

	Mean	Std.Dev.	$\sqrt{1-R^2}$	Target MDE	Required N for MDE
Variable					
HbA1c after 180 days	8.58	1.74	0.66	10%	55
HbA1c after 365 days	8.56	1.67	0.66	10%	56
Weight after 180 days	228	64	0.96	10%	228
Weight after 365 days	228	64	0.96	10%	228
Hospital Visit (Inpatient or ED) 0-180 days	0.39	0.49	0.85	30%	397
Hospital Visit (Inpatient or ED) 0-365 days	0.48	0.50	0.87	30%	278
Hospital Visit (Inpatient or ED) 90-365 days	0.40	0.49	0.92	30%	447

Table 2: Statistical Power to Detect Targeted Minimal Detectable Effects (MDE)

[figure not shown]
9.2 Data Management

9.2.1 Data Collection and Storage

Only approved study staff will have access to data collected for this research.

Administrative data are collected by Geisinger's data broker. For the prospective RCT, under a Data Use Agreement reviewed by the Privacy Office/ISO, a limited dataset stripped of personal identifiers will be transferred securely to MIT.

For the retrospective data exploration, PHI will be de-identified in accordance with a limited data set as allowed by the Research Collaboration Agreement between Geisinger and MIT. The historical data includes diabetic subjects and their household members from Northumberland,

Mifflin, Juniata, and Lackawanna counties where our goal is to compare program participants to non-participants as described above.

Once the data set is sent to MIT, the research team will review it for analysis. The resulting analytic file will be stored in a password-protected database on MIT's secure network. Only research team members can access the data files. The research team members will review the charts and gather all the needed information.

[figure not shown]
The limited dataset for the prospective portion of the study will also include dates of service and ZIP codes.

It will also include information relevant to all encounters:

- Admissions/discharges, clinical procedures, medications administered, problem list entries, and lab values
- Baseline demographic variables of patients (age, sex, ethnicity, payer, comorbidities)
- FFF Program participation

Paid claims summed over various categories of care and timeframes around program entry are requested from Geisinger Health Plan as well.

The FFF program provides food for the entire household. As a result, we are requesting data on household members as well. For the prospective study, household members are identified by the subject to ensure an accurate listing of household members who are actively benefiting from the program. Pulling data using the same address may lead to including household members who are not actively living in the residence (e.g. college student who is not living at home). FFF plans to ask members about their family members in the future, and this will be used to check the household record extraction as well. Data will be provided to MIT with an encrypted household identifier. While we will not have follow-up visits with family members, we aim to observe clinical measures as they appear in the electronic health record. Household IDs will facilitate this analysis.

The retrospective data analysis will include the same data as the prospective study; however, household members will be identified by a shared home address due to no patient contact.

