8.2 Study Population

8.2.1 Approximate Number of Subjects

[figure not shown]
Approximately 500 Geisinger subjects will participate in this study with about half assigned to the treatment group and about half to the control group. Approximately 2000 household members will be included in the data-only portion of the research.

There are 3 groups of subjects identified in this prospective protocol.

Group 1- Will be randomized to the treatment ("Begin Now") group for the FFF program. Subjects will be consented to join the FFF study prior to learning their program start date. They will join the FFF program right away when the program opens in their geographic area. Data will be collected during the first 12 months of subject participation and EHR and claims data may be analyzed for an additional 12 month follow-up period (24 months in total).

Group 2- Will be randomized to the control ("Begin Later") group for the FFF program. These subjects will be consented to join the FFF study prior to learning their program start date. They will join the FFF program approximately 6 months after the program opens in their geographic area. Data will be collected during the first 6 months of subject participation and used as control data for the study. EHR and claims data may be analyzed for an additional 12 month follow-up period (24 months in total from the start of the trial).

Group 3- Household Member data. Consented subjects will be asked for the names and dates of birth (DOB) of individuals living in their household who will be consuming food and benefiting from the FFF program. A waiver of consent is being requested in order to access health

information from the household members' medical records. EHR and claims data may be analyzed 24 months from the start of the trial by a household member.

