Geisinger Health piloted the FFF in Shamokin, PA, and plans to expand the program in the coming months, first in Scranton, PA and then in Lewistown, PA. The program faces capacity constraints such that the program cannot be offered to all eligible participants on the first day. We will carry out a pragmatic randomized controlled trial; eligible patients who are randomized to the treatment group will begin the FFF program immediately, while those randomized to the control group will begin the FFF program 6 months later. This will allow a rigorous examination of the effects of the program for outcomes 6 months after randomization (when the treatment group has been in the FFF program for 6 months and the control group has not yet started the FFF program).

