## 3.3. Secondary outcomes

### *6-month outcomes*

Secondary outcomes of interest include other biomarkers at 6 months: fasting glucose, weight, BMI, blood pressure, total cholesterol, LDL cholesterol, and triglycerides.

We will also examine outcomes based on self-reported survey data, including diet, exercise, and other healthy behaviors, self-efficacy, self-assessed physical and mental health, and patient satisfaction with Geisinger Health as a whole. We will also measure whether the patients have improved their understanding of diabetes and healthy eating.

Other outcomes help us understand the nature of the services offered. The control group has access to dietitian consultations and diabetes self-management classes as part of the standard of care, but we believe the take-up of such services will be higher among the treatment group. We ask about these consultations and classes in the patient surveys to verify that this is the case. We also survey participants about adherence to diabetes best preventive care and whether the subjects are signed up for SNAP benefits, as the program encourages take-up.

Using encounter data, we will also document the level of engagement with the program at the FFF clinic, including the number of weeks that the participants picked up food, the number of dietitian encounters, and the number of classes taken.

Health care utilization is another important secondary outcome. We will examine, at six months, the difference between the treatment and control group in: probability of any inpatient stay, any ED visit, any hospital visit (inpatient or ED). We will also examine the number of such visits, as well as the number of outpatient visits outside the FFF program. We will also examine medication usage, including insulin. Related, we will test for differences in paid claims both in those categories and in the amount paid among the Geisinger Health Plan beneficiaries and check that treatment and control are balanced on inclusion in this sample. We expect there may be outliers in payments, so we will estimate models in levels, logs, and check for differences in the distribution including the median. Any effect of the program on such outcomes may take time to materialize and thus may not be visible at 6 months.

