# 4. Empirical Model

Our initial analysis will estimate intent-to-treat models using linear regression. Consider an outcome,  $Y_i$ , such as HbA1c, for each subject i. The primary specification is:

$$Y_i = \beta_0 + \beta_1 1(\text{Treatment})_i + \beta_2 X_i + \varepsilon_i$$

For our analysis,  $1(\text{Treatment})_i$  is an indicator equal to one if the subject was randomized to the treatment group and zero if the subject was randomized to the control group;  $X_i$  is a vector of control variables. These control variables should be uncorrelated with the treatment indicator, but they can aid in the precision of the estimate because they are correlated with the outcome Y. First, we will include strata indicators for location and HbA1c category. We will also include the lag of the dependent variable, which substantially improves power: for clinical test results that would be the most recent test result prior to enrollment in the study. For utilization outcomes such as inpatient visits, we will include the number of such episodes observed in the 12 months prior to study enrollment.

We also plan to include standard demographic controls: age (5-year age bins), sex (indicator that the patient is male), race/ethnicity (indicators for African American and Hispanic). For the clinical test results, we will also include a control for the number of days from the baseline measure to the follow-up test in order to improve precision. If this number of days is not balanced across treatment and control, we will control for the number of days between the baseline test and the date of enrollment into the study. We will also include the month-year of entry into the study unless this measure is highly correlated with the number of days between blood tests and reduces statistical precision.

We will also estimate models where the outcome is the difference between the baseline and the follow-up exam instead of including the baseline exam result as a control:

$$\Delta Y_i = \beta_0 + \beta_1 1 (\text{Treatment})_i + \beta_2 X_i + \varepsilon_i$$

This is a more restrictive model but may improve statistical precision and requires fewer controls. For models that control for lagged values or in this difference model, we will estimate models for those with non-missing values. We will also test whether missing lagged value is balanced across treatment and control for each measure. Note that all patients have a baseline HbA1c that was used in recruitment.

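### Paid claims are requested as sums around program entry, which falls about 5 to 6 months later in controls; the SAP's cost comparison runs from randomisation, so the request should use that date

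*Protocol*

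**What the plan says.** Protocol 9.2.1 lists the contents of the prospective limited dataset, which includes dates of service, and then adds: "Paid claims summed over various categories of care and timeframes around program entry are requested from Geisinger Health Plan as well". The windows are not listed. The section does not say whether they lie before or after entry, or how a subject without an entry date is handled.

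The footnotes to the events table in Protocol 8.4.1 date program entry. For treatment patients, "FFF program start will occur within 1 month after consent for" them; for control patients, "FFF program start will occur approximately 6 months after consent for" them. Protocol 8.2.1 dates control entry from a different event: "They will join the FFF program approximately 6 months after the program opens in their geographic area".

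The SAP uses another clock:

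- Section 2, on the delayed-start design: "This will allow a rigorous examination of the effects of the program for outcomes 6 months after randomization".
- Section 3.3, on utilisation: "We will examine, at six months, the difference between the treatment and control group in" inpatient, ED and hospital visits. On cost, "we will test for differences in paid claims both in those categories and in the amount paid among the Geisinger Health Plan beneficiaries".
- Section 4, on the baseline covariate for utilisation outcomes: "we will include the number of such episodes observed in the 12 months prior to study enrollment".

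Protocol 8.2.1 also measures the control group's total EHR and claims follow-up (24 months) from the start of the trial, not from program entry.

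**The concern.** In a delayed-start trial the date of program entry is part of what is randomised. Sums anchored on it cover different stretches of trial time in the two arms. Three things follow if the request is carried out literally with the same windows in each arm.

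- The post-entry sums compare treatment subjects on the program with control subjects who are by then also on the program. The off-program months that make controls a comparison group are not in the control window.
- The pre-entry year of a control contains about six months of trial follow-up, so it is not the pre-enrolment baseline the SAP asks for.
- A randomised plan member who never starts has no anchor date, although the intention-to-treat analysis includes that person.

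At stake is the cost part of Specific Aim 2. SAP 3.1 presents the plan's claims as the source that captures care at providers other than Geisinger, so EHR data do not fully replace them.

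**Working it through.** The documents give no sample size, power or effect for paid claims, so there is no plan figure to reproduce. The check is how far entry-anchored windows cover the trial time that the SAP analyses.

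**Inputs**

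- Day 0 is consent and randomisation, which occur in the same recruitment call (SAP section 2, Enrollment & Randomization).
- Treatment entry is at day 0 to 30 (Protocol 8.4.1).
- Control entry is at day 150, 180 or 210. The documents say only about 6 months; the range of plus or minus 30 days is my assumption.
- The target window for the 6-month comparison is trial days 0-180.

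**Formula**

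For entry on day E and a window from day a to day b, overlap = max(0, min(b, 180) − max(a, 0)) / 180.

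| Arm and window | Entry day | Trial days covered | Overlap with days 0-180 |
|---|---|---|---|
| Treatment, 180 days after entry | 0 | 0 to 180 | 180/180 = 100% |
| Treatment, 180 days after entry | 30 | 30 to 210 | 150/180 = 83% |
| Control, 180 days after entry | 150 | 150 to 330 | 30/180 = 17% |
| Control, 180 days after entry | 180 | 180 to 360 | 0/180 = 0% |
| Control, 180 days after entry | 210 | 210 to 390 | 0/180 = 0% |
| Control, 180 days before entry | 150 | −30 to 150 | 150/180 = 83% |
| Control, 180 days before entry | 180 | 0 to 180 | 180/180 = 100% |
| Control, 180 days before entry | 210 | 30 to 210 | 150/180 = 83% |

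**Baseline year**

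In the 365 days before entry, the share that falls after randomisation is E/365. For controls this is 150/365 = 41%, 180/365 = 49% and 210/365 = 58%. For treatment subjects it is 0/365 = 0% to 30/365 = 8%. The SAP covariate requires 0% in both arms.

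**12-month comparison**

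The SAP compares 12 months of exposure with 6. A 365-day sum from entry would follow each starter for the same 12 months after starting, in both arms. For controls it would overlap trial days 0-365 by (365 − E)/365, which is 215/365 = 59%, 185/365 = 51% and 155/365 = 42%.

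**Non-starters**

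E is undefined, so no entry-anchored window exists before or after. Protocol 9.1.1 expects that some treatment subjects may not join; their number is not given.

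**The case against.** A reader might infer that the extract cannot support the randomised cost comparison at all. The documents do not show that. The timeframes are plural, unlisted and placed around entry, so pre-entry sums are allowed, and for controls the 180 days before entry recover 83-100% of trial days 0-180 under the assumed range. The sentence may also serve the retrospective study, for which entry is the natural anchor: 9.2.1 says that study will use the same data as the prospective one. Sums already delivered cannot be re-cut, but nothing prevents a further request.

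A reader might also infer that a real saving would shrink to nothing, or that non-starters will be dropped. Neither is planned. No section proposes comparing post-entry time in one arm with post-entry time in the other. Both documents define the treatment indicator by randomised assignment, and Protocol 9.1.1 intends to record outcomes for all subjects whether or not they participate. Table 2's hospital-visit rates are not paid amounts and cannot size a loss on this outcome.

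These objections limit the point but do not remove it. The pre-entry route needs different windows in the two arms, which neither document specifies. It ends control follow-up on the day the subject happens to start, and it still has no date for a non-starter. The trial-start clock in Protocol 8.2.1 sets the length of follow-up, not the summing windows. Dates of service are listed for the limited dataset but are not said to cover the pre-summed claims. The intention to analyse everyone from randomisation makes the mismatch with the request clearer; it does not supply the missing sums.

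**Conclusion.** The point holds as a mismatch between the data request and the analysis it is meant to feed. The one anchor stated for the claims sums is a post-randomisation date that differs between arms by about 5 to 6 months (about 6 months in controls less 0 to 1 month in treatment). As written, the request does not directly support the SAP's paid-claims comparison by randomised arm. Identical post-entry windows would leave the control window with 0-17% overlap with the period of interest. A pre-entry window for controls would be an approximate repair that omits non-starters.

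The percentages rest on an assumed control entry at days 150-210 and on consent and randomisation falling on the same day. The two descriptions of control entry in the protocol, from consent (8.4.1) and from program opening (8.2.1), also need reconciling, because they give different anchor dates for anyone enrolled after opening.

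The scope is narrow: a secondary outcome in plan members only, whom SAP 3.1 expects to be more than half of subjects and describes as a selected sample. The HbA1c primary endpoint and utilisation from dated EHR encounters are unaffected. It is worth correcting before extraction, but it does not threaten the main result.

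**What to change.** In Protocol 9.2.1, request the paid-claims sums by days from the randomisation/consent date, with identical windows in both arms, for every randomised plan member whether or not they start the program. The windows should be the 12 months before, and days 0-180, 90-180, 0-365 and 90-365 after, which match the SAP's baseline covariate and its 6- and 12-month timeframes. Keep entry-anchored sums for description and for the retrospective study.

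The cost is a change of wording and a small change to the data request, with no added patients, visits or procedures. The enrolment date should already be held, since SAP section 4 uses study-entry timing among its covariates. The change should be made before the extract is run, because delivered sums would need a new request to re-window.
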